11.4 Post-Procedure Care/Discharge (+7 days)

Following the index procedure, the site will notify the sponsor of the subject enrollment status (i.e., whether the subject was enrolled or was a screen failure).

In addition to the standard-of-care procedures at each participating site, all subjects will undergo these assessments at time of discharge (+ 7 days):

1. Concomitant Medications (recommended):

Post Procedure: Clopidogrel bisulfate (Plavix®) – 75 mg qd
or
Ticlopidine (Ticlid®) – 250 mg b.i.d.

After Discharge: Aspirin – 75-325 mg qd indefinitely
Clopidogrel bisulfate (Plavix®) – 75 mg qd for at least 30 days

or
Ticlopidine (Ticlid®) – 250 mg b.i.d. for at least 30 days

2. Adverse Event Monitoring

3. Quality of Life Assessment: SF-36 & EQ-5D

4. Duplex Ultrasound*: This must be completed of the radial artery that was used as the access site during the index procedure. Refer to the Core Lab reference manual for guidelines on performing and submitting this assessment.

If a hospital's standard-of-care requires additional imaging assessments prior to discharge that are not required per the study protocol, copies should be sent to the Core Lab.

Upon discharge, subjects must be given a Stent Implant Card with specific "MR Conditional" information included.

* Post-procedure duplex ultrasound can be completed any time between discharge and the 30-day follow-up visit per standard practice. If not standard-of-care at the site, this assessment must be completed at discharge.

RADIANT / P21-7701

Version: 7.0 / March 21, 2023

11.5 Recommended Medication Regimen

Pre-Procedure	Aspirin AND Clopidogrel bisulfate (Plavix®) OR Ticlopidine (Ticlid®)	75-325 mg (non-enteric coated water soluble) starting at least 24 hours prior to procedure Loading dose of 300-375 mg within 24 hours pre-procedure Loading dose of 250 mg within 24 hours pre-procedure
During Procedure	Heparin (If administered)	Initial bolus IV with additional boluses to maintain an activated clotting time (ACT) > 250 seconds
Post-Procedure	Clopidogrel bisulfate (Plavix®) OR Ticlopidine (Ticlid®)	75 mg qd 250 mg b.i.d.
After Discharge	Aspirin AND Clopidogrel bisulfate (Plavix®) OR Ticlopidine (Ticlid®)	75-325 mg qd indefinitely 75 mg qd for at least 30 days 250 mg b.i.d. for at least 30 days

The above medications are NOT required. An alternative medication regimen that is standard of care at the institution may be used instead. Any medications utilized must adhere to the recommendation specified by each medication's package insert.

11.6 Follow-up Visit/Assessments

Subjects are required to complete the follow-up visit at 30 days (+/- 7 days) post-procedure **at the investigational site (study institution/office/clinic)**. The following assessments will be completed at this visit:

- 1. Concomitant Medications Assessment**
- 2. Adverse Event Monitoring**
- 3. Quality of Life Assessment: SF-36 & EQ-5D**

NOTE: Please refer to section 11.4 for the requirements and timing of a duplex ultrasound of the radial artery to be done post-procedure.

11.7 Telephone/Virtual Follow-Up

The 30-day follow-up visit may be conducted by telephone or other virtual means of communication (i.e., audio/video conferencing) **ONLY in exceptional circumstances** (e.g., due to COVID infection). If the visit is conducted by telephone/virtually, concomitant medications, safety information and quality of life assessment (SF-36 and EQ-5D) data should be collected from the subject or from a friend/family member, if possible.

Every occurrence of a telephone/virtual 30-day follow-up visit will be captured as a protocol deviation with an explanation recorded as to why the visit was not completed at the site (e.g., due to COVID infection).

RADIANT / P21-7701

Version: 7.0 / March 21, 2023

11.8 Lost to Follow-up

For all active subjects, the site must first make three (3) telephone contact attempts to reach the subject for the 30-day follow-up visit. If unsuccessful, the Investigator must then send a certified letter to the subject. All contact attempts must be adequately documented in the subject's source documents. When possible, the patient's primary care physician should also be asked for assistance with contacting the subject.

The subject will be considered lost to follow-up only under the following circumstances:

- The site learns that all methods of contacting the subject are no longer viable (e.g., telephone number not in service, no forwarding address provided, no current/correct contact information available from the patient's primary care physician).
- The site fails to reach/hear from the subject for the 30-day follow-up visit after all required contact attempts have been made using a valid telephone number and address on record.

11.9 Unscheduled Visits

Unscheduled follow-up visits may be required to ensure the safety of study subjects. All complications and adverse events will be evaluated by the Investigator and reported according to sponsor and EC regulations.

If an unscheduled follow-up visit is required, the site study team will assess if the subject has undergone any interventional treatment or experienced any adverse events since the last protocol-specified visit and will record such information on the appropriate CRF pages. Any additional imaging obtained must be forwarded to the Core Lab. All relevant information required to assess any adverse event reported should be maintained in the subject's medical records and all relevant documentation required for event adjudication should be provided as requested by the sponsor.

Assessments that may be completed at an unscheduled visit include, but are not limited to, the following:

1. **Concomitant medications**
2. **Physical examination**
3. **Imaging studies**
4. **Adverse event monitoring**
5. **Quality of Life Assessment: SF-36 & EQ-5D**

11.10 Subject Study Exit/Discontinuation

Every subject should be encouraged to remain in the study until they have completed the final, protocol-required, follow-up visit at 30 +/- 7 days post-procedure.

As required, the investigator(s)/institution(s) will arrange for the care of subjects after their participation in the study has ended, per institutional standard-of-care and/or the investigator's best clinical judgement.

If subject participation is prematurely discontinued, the reason for such must be documented in the subject's source documents and the CRF. Possible reasons for a subject's early exit from the study may include, but are not limited to, the following:

- **Withdrawal of consent** – Subject decides to withdraw from the study. This decision must be "independent" (i.e., made by the subject). The reason for withdrawal of consent should also be inquired from the subject and documented if provided.
- **Physician discretion** – The Investigator may choose to withdraw a subject from the study for reasons which include, but are not limited to, safety concerns. A detailed reason for the withdrawal should be documented.
- **Death**

RADIANTY / P21-7701

Version: 7.0 / March 21, 2023

- Lost to follow-up – all methods of contacting the subject are no longer viable or the subject is unable to be reached, or heard back from, to complete the 30-day follow-up visit

Subjects who discontinue early from the study will not be replaced and cannot re-enter the study. The investigator(s)/institution(s) must arrange for any continued safety monitoring, treatment and/or follow-up of subjects who withdraw/are withdrawn from the study or determined as lost to follow-up as per standard-of-care/best clinical judgement, unless it has been determined by the Investigator that the continued follow-up may jeopardize the rights, safety, and/or welfare of the subject. The investigator(s)/institution(s) must also maintain traceability of the study device that has been implanted in each of these subjects in the event they are to report any safety-related events or complaints attributed to the study device to the sponsor.

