13.1 Adverse Events

An Adverse Event (AE) is any untoward medical occurrence, unintended disease or injury or any untoward clinical signs, including an abnormal laboratory finding, in subjects, users or other persons, in the context of a clinical investigation, whether or not related to the investigational device and whether or not anticipated. Therefore, all anticipated adverse events listed in **section 13.2** are included within the scope of overall AE reporting requirements.

In this study, the investigational products are:

- S.M.A.R.T. RADIANT
- 9 and 10 mm diameters of SABERX RADIANT

Though subjects are considered enrolled only from the time they are confirmed to qualify for study participation according to the eligibility criteria (i.e., upon completion of angiography), all adverse events for all enrolled subjects, including those from the "roll-in" cohort of the study, will be reported retroactive to when vascular access was established in the radial artery (i.e., time of puncture) until their exit from the study (i.e., point of study completion or premature discontinuation). Each new AE or change to a previously

RADIANT / P21-7701

Version: 7.0 / March 21, 2023

reported AE (based on any new findings) will be recorded and followed until resolution or stabilization of the event or until the subject has exited the study.

Subjects should be encouraged to report AEs spontaneously and may volunteer information at any time. At each evaluation, the Investigator will assess if an adverse event has occurred and will obtain all information required to complete the appropriate AE CRF(s). If an event occurs at an outside institution, the Investigator should obtain all or as much of the required AE information as possible.

For each AE, the Investigator should report at a minimum, the term/description, start/end dates, severity, serious/non-serious classification, treatment and outcome of the AE and determine its causality/association to the study devices or study procedures. During causality assessment, clinical judgement shall be used and the relevant documents, such as the Investigator's Brochure or the study protocol shall be consulted, as all the foreseeable SAEs and the potential risks are listed and assessed there. The presence of confounding factors, such as concomitant medication/treatment, the natural history of the underlying disease, other concurrent illness or risk factors shall also be considered.

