13.3 Serious Adverse Events

A Serious Adverse Event (SAE) is any AE that led to any of the following:

- a) death
- b) serious deterioration in the health of the subject, that resulted in any of the following:
 - life-threatening illness or injury;
 - permanent impairment of a body structure or a body function;
 - hospitalization or prolongation of existing hospitalization;
 - medical or surgical intervention to prevent life-threatening illness or injury or permanent impairment to a body structure or a body function;
 - chronic disease
- c) fetal distress, fetal death or a congenital physical or mental impairment or birth defect

The Investigator must report all new SAEs or changes to previously-reported SAEs (based on any new findings), with whatever information is available at the time, to the sponsor and/or designee by any acceptable method as communicated by them, within 24 hours or one working day of first awareness of the event by any member of the site study team and provide any additional information as required by the sponsor/designee. Principally, such events may be reported through the EDC system within 24 hours or one working day of first awareness; if this is not possible, the event must still be reported in the EDC system as soon as possible. In the case of death, all available information, e.g., autopsy or other post-mortem findings, including causality/association to the investigational product, should be provided. The medical monitor of this study will decide if more follow-up information is needed in case the event is not resolved at the time of subject exit from the study.

The Investigator or Contract Research Organization (CRO) shall notify the EC of the institution at which SAEs occurred (and/or the ECs of other participating institutions) in accordance with institutional requirements.

SAEs will be recorded and followed until resolution or stabilization of the event or until the subject has exited the study.

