13.6 Device Deficiencies

A device deficiency is any inadequacy in the identity, quality, durability, reliability, safety or performance of an investigational device, including device malfunction, use errors or inadequacy in information supplied by the manufacturer.

- A device malfunction is considered a failure of a device to meet any of its performance specifications or otherwise perform as intended. Performance specifications include all claims made in the Instructions for Use (IFU)/Investigator's Brochure (IB)/clinical study protocol.

In the event of a device deficiency, detailed information on the product, circumstances of the deficiency as well as any complications and their management will be collected and reported.

Though subjects are considered enrolled only from the time they are confirmed to qualify for study participation according to the eligibility criteria (i.e., upon completion of angiography), all device deficiencies for all enrolled subjects, including those from the "roll-in" cohort of the study, will be reported retroactive to the initial use or handling of a study device until their exit from the study (i.e., point of study completion or premature discontinuation).

The Investigator must report all new device deficiencies or changes to previously-reported device deficiencies (based on any new findings), with whatever information is available at the time, to the sponsor and/or designee by any acceptable method as communicated by them, within 24 hours or one working day of first awareness of the event by the study team at the institution and provide any additional information as required by the sponsor/designee. If the event is not reported through the EDC system within this time

RADIANTY / P21-7701

Version: 7.0 / March 21, 2023

period, it must be done so as soon as possible. If applicable, the Investigator must make arrangements for the safe return of any malfunctioned, damaged, and/or unused investigational devices in accordance with the instructions provided by the sponsor.

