14.5 Missing Data

For both primary endpoints, a sensitivity analysis will be done where missing data is imputed using a worst-case scenario. Specifically, for the efficacy endpoint (technical success), missing data will be imputed as "unsuccessful." Likewise, missing safety data will be imputed to indicate that the subject experienced a radial access-related AE.

For secondary endpoints, no imputation of missing data is planned since these endpoints are hypothesis-generating and not being used to expand labeling. Subjects who have ascertainment of status at a later out-of-window date (for example, subjects who are known to be free of events past discharge but missed

RADIANT / P21-7701

Version: 7.0 / March 21, 2023

the discharge visit) are not considered missing as their status is known and their data will be used as noted previously.

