## 11 HANDLING OF MISSING DATA

For both primary endpoints, a sensitivity analysis will be done where missing data is imputed using a worst-case scenario. Specifically, for the efficacy endpoint (technical success), missing data will be imputed as “unsuccessful.” Likewise, missing safety data will be imputed to indicate that the subject experienced a radial access-related AE.

If after imputing the missing data with the worst-case scenario, the interpretation of the analysis changes, then each missing data point will be imputed one at a time and the analysis re-run each time in order to see how many failed data points were needed to change the interpretation.

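### Adverse event collection ends when an investigator withdraws a subject for safety concerns, so the descriptive 30-day safety rates can be understated

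*Protocol*

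**What the plan says.** **Who may leave.** Protocol 11.10 lists reasons for early exit. One is physician discretion: "The Investigator may choose to withdraw a subject from the study for reasons which include, but are not limited to, safety concerns". The withdrawal is from the study. Subjects who leave early are not replaced and cannot re-enter.

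**What stops at exit.**
- Protocol 13.1 has adverse events reported from radial puncture "until their exit from the study (i.e., point of study completion or premature discontinuation".
- Protocol 13.3: "SAEs will be recorded and followed until resolution or stabilization of the event or until the subject has exited the study". Sections 13.4 and 13.5 use the same limit for major adverse events and unanticipated serious adverse device effects.
- Protocol 13.6: device deficiencies "will be reported retroactive to the initial use or handling of a study device until their exit from the study".

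**What continues after exit.** Protocol 11.10 adds: "The investigator(s)/institution(s) must arrange for any continued safety monitoring, treatment and/or follow-up of subjects who withdraw/are withdrawn from the study". This is by standard of care or clinical judgement, and the investigator may set it aside if it could harm the subject. The site must also keep the implanted device traceable in case the subject later reports a device-attributed event. Under 13.3 the medical monitor "will decide if more follow-up information is needed in case the event is not resolved at the time of subject exit from the study".

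**How the data are used.** The primary safety endpoint closes at hospital discharge (Protocol 8.1.1, SAP 4.1). For both primary endpoints, SAP section 11 says "a sensitivity analysis will be done where missing data is imputed using a worst-case scenario". The 30-day secondary safety rates are per subject and are not formally tested (Protocol 8.2.1 and 14.4.2, SAP 8.4.2). Protocol 14.5: "For secondary endpoints, no imputation of missing data is planned". Neither document states the denominator for subjects who leave before day 30.

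**The concern.** Withdrawing a stented subject from this study removes no exposure. It removes only the rest of the 30-day observation. When the reason is a safety concern, the loss falls on subjects the investigator already judges to be at risk, so the missing data are plausibly related to the outcome.

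Take a subject withdrawn on day 5 who dies or needs target lesion revascularization on day 15. No passage requires that event to be entered in the study data. The 30-day rates would then describe safety while the investigator kept the subject in the study, whereas the objective is acute safety in the treated population. These rates are the study's own evidence on death, amputation and revascularization in a pivotal, pre-market trial, even though they are not tested.

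**Working it through.** **1. The plan's own figure.** Inputs from Protocol 14.3 and SAP section 5: n = 129, assumed complication rate 2%, performance goal 7%, one-sided exact 95% Clopper-Pearson bound.
- Upper bound for 4 of 129 events: 6.95%, a pass. For 5 of 129: 7.98%, a fail. The largest passing count is 4.
- Power = P(X ≤ 4) for Binomial(129, 0.02) = 0.882. Type I error = P(X ≤ 4) for Binomial(129, 0.07) = 0.048.

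The stated 88% reproduces, and nothing in this point alters it.

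**2. Which events can be lost.** The event that prompts withdrawal occurs before exit and is recorded under 13.1. In the per-subject rate of any adverse event that subject already counts. At risk are first events of another type after exit: mainly death, amputation, target lesion revascularization and later complications. Deficiencies of the sheath, balloon and delivery system arise mostly during the index procedure, when these are used and removed (Protocol 11.1), so little is lost there beyond the implanted stent.

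**3. Size for a 30-day rate.** Let w be the number of subjects withdrawn for safety and q their risk of a later, uncollected first event of the type in question. Neither is in the documents, so both are assumed. If these subjects stay in the denominator as event-free, the shortfall is w × q / 129, in percentage points:

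| w | q = 10% | q = 30% | q = 50% |
|---|---|---|---|
| 1 | 0.08 | 0.23 | 0.39 |
| 2 | 0.16 | 0.47 | 0.78 |
| 4 | 0.31 | 0.93 | 1.55 |
| 6 | 0.47 | 1.40 | 2.33 |

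If they are dropped from the denominator instead, and the remaining subjects have rate r, the shortfall is w × (q − r) / 129. With w = 6, q = 50% and r = 1%, that is 6 × 0.49 / 129 = 2.28 points. In that case the rate is too low only if the withdrawn subjects have a higher risk than the rest.

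For scale, one unrecorded event is 1/129 = 0.78 points. The 30-day death rates in Protocol 1.3 are 0.0% and 1.0% (femoropopliteal) and 2.0% and 1.4% (iliac).

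**4. Primary safety endpoint.** An event is lost only if the subject is withdrawn while in hospital and a first major access-site complication follows before discharge. If status is then missing:
- Counted as an event (the planned sensitivity analysis): with 1 missing, at most 4 − 1 = 3 observed events still pass; with 2 missing, at most 2.
- Dropped: the upper bound for 4 of 128 is 7.008%, a fail, where 4 of 129 passes at 6.955%. The largest passing count falls to 3, and the chance of passing at a true 7% falls from 4.8% to 1.9%.

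Both make the test harder to pass.

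**The case against.** The strongest reply is that little can be lost, and only from endpoints that carry no test. Protocol 14.5 calls the secondary endpoints hypothesis-generating and not intended to expand labeling. The prompting event is already on record. Subjects are to be encouraged to stay, the reason for exit must be documented, and continued safety monitoring must be arranged. Protocol section 13 obliges anyone who identifies a safety matter to inform the investigator and the sponsor. Protocol 14.5 also uses status learned at a later, out-of-window date instead of treating it as missing.

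Most of this stands, and it limits the point to new events after exit. It does not close the gap. Monitoring under 11.10 is standard of care, with an opt-out and no instruction to enter findings in the study data. Traceability is passive and concerns events attributed to the device, whereas death is defined as all-cause (Appendix A). The medical-monitor clause concerns events already reported. The out-of-window rule helps only if someone looks.

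A reader might infer that the primary safety rate is also biased downward and that a false pass becomes more likely. The documents do not support that. The endpoint closes at discharge. Missing status is imputed as an event in the sensitivity analysis, and SAP section 11 adds one-at-a-time re-imputation if the interpretation changes. A raised pass rate would require a sizeable share of complications to be lost in hospital and those subjects to be kept as event-free; no passage indicates either.

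**Conclusion.** The concern holds for the 30-day secondary safety rates. New events between a safety-related withdrawal and day 30 may go unrecorded, and those rates can be understated. It cannot be said that they will be: that depends on how many subjects are withdrawn and on their later risk, and the documents give neither. Under the assumed ranges (1 to 6 withdrawals, 10% to 50% later risk, subjects retained as event-free) the shortfall is about 0.1 to 2.3 percentage points.

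The hypothesis tests, sample size and power are unaffected. The primary safety endpoint is exposed only through exit before discharge.

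Two further inferences should be resisted. Expressing one lost death as a share of the deaths expected from the iliac literature rates would apply those rates to all 129 subjects, although the trial also enrolls femoropopliteal subjects, for whom Protocol 1.3 cites 0.0% and 1.0%. Nor does the point require removing safety concerns as a ground for withdrawal, or making missing status an event in the primary analysis. The defect is that withdrawal also ends safety data collection.

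**What to change.** **Protocol 11.10, 13.1 and 13.3 to 13.6.** Separate ending study assessments from ending safety data collection. For every enrolled subject withdrawn by the investigator, and unless the subject withdraws consent, collect adverse events, device deficiencies, vital status, index limb amputation and target lesion revascularization to day 30, by chart check or telephone. Use these data in the 30-day rates. Section 11.3 already provides the model: subjects who receive no stent are followed for safety to 30 days and excused from the scheduled 30-day assessments. Align the wording on exit in the listed sections.

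**SAP 8.4.2 and 11.** State the denominator for subjects who leave before day 30. Add a sensitivity analysis for them, for example showing each 30-day rate with unknown status counted first as event-free and then as an event.

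**Leave unchanged.** Investigator discretion over withdrawal, and worst-case imputation of the primary endpoints as a sensitivity analysis.

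**Cost.** A wording amendment, a short SAP addition, and a chart check or call for what should be a few subjects, whose monitoring the site must in general already arrange. Reported event rates may come out slightly higher.
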